3.1. Center Recruitment

Participation is voluntary and without financial incentive. The study will be promoted through web and social media channels to share study protocol and information to potentially interested investigators. The project will be presented during national and international anesthesiology conferences and symposia.

3.2. Study duration

The overall duration of the study is 18 months, with 9 months allocated for enrollment and data collection, and 9 months dedicated to statistical analysis. Participating hospitals have to prospectively collect data in a consecutive manner within a predefined period of 1 week. Participating hospitals can decide on which period they choose to collect data, but data collection must take place during a predetermined time window of 8 weeks.

4. STUDY POPULATION

4.1. Population (base)

Patients subjected to invasive mechanical ventilation (IMV) during general anesthesia for surgery will be included in a consecutive manner.

4.2. Inclusion criteria

Patients are eligible if:

- adults:
- receiving intraoperative IMV (via tracheal intubation, or supraglottic device) during general anesthesia for surgery.

4.3. Exclusion criteria

The following patients will be excluded:

- subjected to IMV outside of an operating room; and
- subjected to IMV during extracorporeal life support.

4.4. Sample size calculation

The sample size estimation for the multicenter data-registry was carried out focusing on the main outcome, the PPCs rate of incidence among patients subjected to IMV during general anesthesia for surgery. Initial results presented in existing research highlighted an event rate around 10% (4); Figure 1 was used to determine the size of the study through a method focused on optimizing the precision of the estimates in terms of Confidence Interval (CI) width. The calculation indicates that a sample size of 10,000 subjects will achieve a confidence interval width of 0.0119, as shown in Figure 1. The Clopper-Pearson method was employed for this estimation process, as a more conservative solution.

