Prospective collection of demographic data, ventilation settings and ventilation parameters, and outcomes means the risks are negligible and the burden is minimal.

Data collection

- Informed consent and data of admission
- Demographic and clinical characteristics
- Characteristics of the surgical procedure (elective vs non-elective, cardiac vs non-cardiac, open vs minimally invasive)
- The type of anesthesia (involving volatile anesthetic medications or intravenous agents)
- Mechanical ventilation settings and respiratory system mechanics variables
- Monitored parameters (peripheral oxygen saturation, end-tidal carbon dioxide tension, arterial blood gases if available, mean blood pressure, systolic and diastolic blood pressure, and heart rate)
- Extubation procedure
- Peri- and postoperative variables and outcomes
- Follow up to the fifth postoperative day
- In-hospital death and hospital length of stay on 28th day after surgery.

Sample size

Considering a PPCs incidence around 10% as found in previous research, at least 10000 patients are needed to achieve a confidence interval width of 0.0119.

Statistical analysis

Variables will be reported as mean and standard deviation or median and interquartile

range according to the normal or non-normal distribution. Also, the comparisons among variables will be carried out through student T-test or Mann- Whitney U test according to data distribution. As regards as categorical variables, proportions will be reported and comparisons will be performed by the Chi-square or Fisher exact test as appropriate. The following planned secondary analyses will be carried out:

- Cardiac vs non-cardiac surgery
- Elective vs non-elective procedures
- Practice of weaning from invasive mechanical ventilation
- Open vs minimally invasive/robotic surgery
- Comparison among the different obesity classes
- Obese vs non obese patients
- Impact of geo-economical difference

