6. STATISTICAL ANALYSIS

The demographic and baseline characteristics of the study population will be reported. Continuous variables will be summarized using median and interquartile range (IQR), and categorical variables will be summarized using frequencies and percentages. The comparison among groups for categorical variables will be performed by considering the Chi-square test or Fisher's exact test whatever is appropriate; for continuous variables, the Wilcoxon -Rank Sum test will be used.

The primary endpoint, namely, the PPCs rate, will be calculated together with the 95% confidence interval (CI). Moreover, the impact of the patient's characteristics on the risk of PPCs will be handled by using appropriate statistical models, such as Logistic Regression. These analyses will be adjusted for potential confounders identified at the study's outset, providing insights into factors that may influence PPCs rates among the patients population subjected to surgery. The 95% CIs on the model OR (Odds Ratios) and predicted probability of PPCs, according to the patient's profile, will be estimated. Handling of missing data will be addressed through robust methods like multiple imputation or complete case analysis, depending on the nature and extent of the missingness. Sensitivity analyses will further assess the robustness of the findings, examining how different assumptions about the missing data and analytical methods influence the results.

The significance of differences will be defined by the p-values, with a value of less than 0.05 considered statistically significant.

The following planned secondary analyses will be performed:

- Cardiac vs non-cardiac surgery
- Elective vs non-elective procedures
- Obese vs non-obese patients
- Open vs minimally invasive/robotic surgery

- Comparison among the different obesity classes
- Practice of weaning from invasive mechanical ventilation
- Impact of geo-economical difference

The analyses will be performed by using R 3.4.2.

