13. FIGURES

Figure 1. 95% confidence interval width according to sample size

[figure not shown]
[figure not shown]

Figure 2. Schematic diagram of trial design: procedures and stages

CRF, case report form

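### The 95% CI width of 0.0119 at 10,000 patients holds only for independent patients; sampling whole hospital-weeks makes the real precision worse by an amount the protocol does not state

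*Protocol*

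**What the plan says.** The sample size rests on precision alone. Section 4.4 takes the anticipated incidence of postoperative pulmonary complications (PPCs) from earlier work ("Initial results presented in existing research highlighted an event rate around 10% (4") and concludes: "The calculation indicates that a sample size of 10,000 subjects will achieve a confidence interval width of 0.0119". The Summary repeats this as a requirement: "at least 10000 patients are needed to achieve a confidence interval width of 0.0119". The caption in Section 13 gives the confidence level: "Figure 1. 95% confidence interval width according to sample size". On the method, Section 4.4 adds: "The Clopper-Pearson method was employed for this estimation process, as a more conservative solution".

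Section 3.2 describes how patients enter: "Participating hospitals have to prospectively collect data in a consecutive manner within a predefined period of 1 week". Each centre sets its own dates within an eight-week span, as the same section explains: "Participating hospitals can decide on which period they choose to collect data, but data collection must take place during a predetermined time window of 8". Sections 3 and 3.1 describe voluntary, international recruitment of academic and non-academic hospitals.

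For the analysis, Section 6 says: "The primary endpoint, namely, the PPCs rate, will be calculated together with the 95% confidence interval (CI". It does not name the type of interval. The protocol mentions no number of centres, expected centre size, ICC or design effect.

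**The concern.** Clopper-Pearson is an exact interval for independent Bernoulli observations. Here the unit that enters the study is a hospital-week, and all eligible patients in it come along. Patients in the same hospital share case mix, surgical programme and ventilation habits.

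The protocol itself expects these things to matter. Section 2.1 hypothesises that PPCs depend on patient and surgery characteristics and on ventilator settings. Section 5.2 collects centre characteristics. Sections 2.2 and 6 plan to examine geo-economic differences. An ICC of exactly zero does not fit those premises.

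PPC incidence is the primary endpoint, and the width of 0.0119 is the only quantitative justification given for 10,000 patients. Section 1.2 also says that the results should inform sample sizes of later trials. A reader who takes 0.0119 at face value will think the incidence is known more precisely than the design allows.

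**Working it through.** **Inputs from the protocol.** Anticipated incidence p = 0.10, n = 10,000 and Clopper-Pearson (Section 4.4); 95% level (Section 13, Figure 1 caption); all consecutive patients in one week per hospital (Section 3.2).

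**Inputs assumed, because the protocol gives none.** Patients per centre m = 25, 50 or 100 (that is, 400, 200 or 100 centres), with equal centre sizes; ICC = 0.01 or 0.05.

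**Step 1: reproduce the stated figure.** With x = 1,000 and n = 10,000, the Clopper-Pearson limits are the 2.5% quantile of Beta(1,000, 9,001) and the 97.5% quantile of Beta(1,001, 9,000). These are 0.09419 and 0.10605, so the width is 0.01186, which rounds to 0.0119. The stated figure is therefore the plain binomial width, with a design effect of exactly 1 and no hidden allowance for clustering.

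**Step 2: how much margin Clopper-Pearson adds.** The Wald width is 2 × 1.96 × √(0.1 × 0.9 / 10,000) = 0.01176, and Wilson also gives 0.01176. The margin is 0.01186 − 0.01176 = 0.0001, or less than 1% of the width.

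**Step 3: allow for clustering.** The design effect is DE = 1 + (m − 1) × ICC, and the effective sample size is 10,000 / DE. The Clopper-Pearson width is recomputed at the effective sample size. If a plain binomial interval were reported instead, its approximate coverage would be 2Φ(1.96 / √DE) − 1.

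| m | ICC | DE | Effective n | Width | Coverage of a plain binomial CI |
|---|---|---|---|---|---|
| 25 | 0.01 | 1.24 | 8,065 | 0.0132 | 92% |
| 25 | 0.05 | 2.20 | 4,545 | 0.0177 | 81% |
| 50 | 0.01 | 1.49 | 6,711 | 0.0145 | 89% |
| 50 | 0.05 | 3.45 | 2,899 | 0.0222 | 71% |
| 100 | 0.01 | 1.99 | 5,025 | 0.0168 | 84% |
| 100 | 0.05 | 5.95 | 1,681 | 0.0293 | 58% |

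Worked line: for m = 50 and ICC = 0.01, DE = 1 + 49 × 0.01 = 1.49, the effective n is 10,000 / 1.49 = 6,711, and 1.96 / √1.49 = 1.61, which gives 89% coverage.

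**Step 4: how small an ICC already matters.** The interval widens by 10% when DE = 1.1² = 1.21, that is at ICC = 0.21 / (m − 1). This is 0.0088 for m = 25, 0.0043 for m = 50 and 0.0021 for m = 100.

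**Step 5: unequal centre sizes.** With coefficient of variation cv of centre size, DE = 1 + ((1 + cv²) × m − 1) × ICC. For m = 50, ICC = 0.01 and cv = 0.5, DE = 1 + (1.25 × 50 − 1) × 0.01 = 1.61 instead of 1.49. The width becomes about 0.0119 × √1.61 = 0.0151 instead of 0.0145.

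**The case against.** Several counter-arguments have weight.

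- **The arithmetic is right.** A reader might infer that Section 4.4 contains a calculation error. It does not; 0.0119 reproduces exactly. The fault is the unstated independence assumption.
- **The size is not in the protocol.** All widths above rest on assumed m and ICC. With 25 patients per centre and ICC 0.01 the width is 0.0132, a modest loss; 58% coverage is the single worst corner of the grid. This stands, so the sponsor should use its own expected centre size rather than copy these figures.
- **Section 6 names no binomial interval.** Clopper-Pearson is tied to the sample-size step only. A reader might infer that the published interval will undercover, but the documents do not support that: the interval method may be set in a statistical analysis plan that is not shown. The coverage figures are conditional. The width in Section 4.4 is different, because it is the protocol's own claim and no later analysis choice can make it true under clustering.
- **Describing Clopper-Pearson as conservative is true among binomial methods.** It is slightly wider than Wald and Wilson, and the protocol does not claim that it protects against clustering. The only risk is that a reader takes it as a general safety margin.
- **Hospitals volunteer and are not drawn at random.** A design-effect calculation then treats them as if sampled from a wider population of similar hospitals, and it does not correct for self-selection. If inference stopped at the participating hospitals, the case would be weaker. Section 1.2, with its worldwide aim and its use for later trials, points beyond them.
- **The endpoint is descriptive.** No power claim or decision threshold depends on 0.0119, and even the worst corner is about ±1.5 percentage points around 10%. This limits the consequences but does not make the statement correct.

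**Conclusion.** The concern holds as a fault in the stated precision. The width of 0.0119 is the independent-patient width, and the design samples hospital-weeks. For any positive ICC, and for inference beyond the participating hospitals, the true precision is worse, and the 0.0001 margin from Clopper-Pearson does not cover the gap.

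The direction is certain under those conditions; the size is not. As an illustration with equal centres, 25 to 100 patients per centre and ICC 0.01 to 0.05, the width is about 0.013 to 0.029, or 1.1 to 2.5 times the stated one (0.0132 / 0.0119 to 0.0293 / 0.0119). Unequal centre sizes widen it further.

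A reader might also infer that 10,000 patients are too few. The protocol does not support that either: it gives no reason why a width of 0.0119 in particular is needed, so the number can stay once its precision is described correctly.

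**What to change.** Keep 10,000 patients and change the wording in three places.

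1. **Section 4.4 and the Summary.** State that 0.0119 is the width under independence. Add the width after a design effect of 1 + (m − 1) × ICC, using the sponsor's own expected number of patients per centre and a stated ICC range, with an allowance for unequal centre sizes.
2. **Section 4.4, remark on Clopper-Pearson.** Limit it to the comparison with other binomial intervals, so that it does not read as a margin covering clustering.
3. **Section 6.** State that the 95% CI for the primary PPC rate accounts for centre. Options are a cluster-robust or survey-type interval with centre as the sampling unit, or Clopper-Pearson on the effective sample size. If an analysis plan already says so, a cross-reference is enough.

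The cost is a few sentences and no extra patients or data. The drawback is that the stated precision becomes less favourable.

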5. METHODS

5.1. Study Outcome

5.1.1. Primary outcome

The primary endpoint is to report the number of patients with PPCs, considered as a composite incidence of predefined postoperative pulmonary complications occurring in the first 5 postoperative days or hospital discharge whichever comes first, examining also individual PPCs incidence and type (for the definitions of PPCs see '11').

5.1.2. Secondary outcomes

Secondary endpoints include: 1) ascertaining the practice of mechanical ventilation in patients undergoing general anesthesia for surgery including key intraoperative ventilator characteristics and respiratory system mechanics; 2) describing the incidence and type of IAEs; 3) describing postoperative complications other than PPCs in the first 5 postoperative days or hospital discharge whichever comes first; 4) describing the impact of intraoperative hemodynamic management on the occurrence of PPCs; 5) reporting intensive care unit (ICU) admission and length of stay, hospital length of stay, and hospital mortality on day 28.

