Weaning phase: at beginning and at the end of weaning phase, the following variables will be acquired: ventilatory mode, Vt (ml), PEEP (cmH₂O), pressure support over PEEP (if any) (cmH₂O), inspiratory trigger regulations, FiO₂, respiratory rate (breaths/min), SpO₂ (%), EtCO₂(mmHg or kPa), mean, systolic, and diastolic arterial pressure (either invasive or non-invasive), mmHg, heart rate (beats per minute).

It will also be recorded if aspiration is performed prior to tube removal. The number and type of IAEs will be acquired throughout the whole duration of surgical and anesthesiologic procedures (see "11" for definitions).

Peri-operative variables: duration of anesthesia procedure, duration of surgical procedure, tube type and size, type of anesthesia, type of analgesia (total endovenous, antibiotic prophylaxis, details on neuromuscular function monitoring and about the use of reversal agents (if any), total intra-operative fluid and total transfusion of blood products, temperature and hemoglobin at end of surgery (if clinically available). The possible admission to post-anesthesia care unit (PACU) and the eventual administration of non-invasive respiratory support (NIRS), namely, high flow oxygen therapy, continuous positive airway pressure, and non-invasive bilevel positive airway pressure ventilation, and the settings will be recorded.

Post-operative variables: vital signs involving SpO₂, heart rate, systolic, diastolic, and mean arterial pressure, body temperature if assessed, eventual arrythmias occurrence, and the blood gas analysis parameters (optional assessment) will be hourly collected in the immediate post-operative period or PACU stay, and at the discharge to surgical ward or ICU.

Follow up (day 0 to 5): PPCs are recorded from the medical chart on day 0 (end of surgery to 23:59h) and on days 1,2,3,4 and 5 post-operative (each day runs from 00:00 AM to 23:59 PM). Follow–up is completed on the day of discharge or on day 5 if the patient is still admitted.

On day 0 the following variables are collected: IMV after discharge from the operation room, admission to ICU/PACU after surgery, PPCs (see "11").

On day 1,2,3,4 and 5 the following variables will be collected: any new admission to ICU; any new or prolonged IMV; PPCs (see "11").

The data mentioned above are considered essential to defined as "complete" each patient's medical record.

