ICU or PACU admission: recording of data during the critical care submission can be left out by the participating centers if this workload exceeds their possibilities. However, it is requested to collect the ICU/PACU data. In case of IMV and/or admission to the ICU/PACU during the follow-up period (day 0, 1, 2, 3, 4 or 5), the following variables will be collected on a different CRF: reason for ICU/PACU admission, reason for IMV or NIRS, APACHE II score (24), on (first) admission to and within the first 24 hours in ICU (i.e., the APACHE II score to be collected and reported for patients who were in the ICU before surgery, and were referred to the ICU after surgery, starts direct after the first admission to the ICU; the APACHE II score to be collected and reported for patients who were not in the ICU before surgery, but were referred to the ICU after surgery, starts direct after surgery, in the ICU). At the first hour of ICU/PACU admission and in case of continued admission each day (during morning rounds) the following variables are collected: SOFA score, IMV regulations, arterial blood gas values (pH, PaCO₂, PaO₂ if available), closest to 08:00 AM, PPCs (number and type, see "p 11"), extra-pulmonary organ failure (number and type), and risk factors for respiratory failure (number and type).

If a patient is transferred back to the ward, the non–ICU/PACU follow–up CRF will be used to record the variables of the remaining follow–up days.

Follow up (day 28): On day 28 ICU and hospital length of stay as well as in hospital death are assessed.

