11.3. Definition of other postoperative complications

Other postoperative complications that will be assessed include: sepsis of non-pulmonary genesis, defined as a life-threatening organ dysfunction following non-pulmonary infection, deep venous thrombosis more or less associated to pulmonary embolism as assessed through ultrasound more or less accompanied by CT scanning, myocardial infarction, acute pulmonary edema, cardiac arrest, acute kidney injury

defined as an increase in serum creatinine by $\geq 50\%$ within 7days or increase in serum creatinine ≥ 0.3 mg/dl (26.5 μ mol/l) within 2 days or oliguria for \geq 6hours, and cerebrovascular accident/stroke.

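### The day 0–5 follow-up list and the complete-record rule omit the non-pulmonary complications of secondary endpoint 3, so their capture on the ward is not assured

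*Protocol*

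**What the plan says.** Section 5.1.2 of the Protocol sets, as its third secondary endpoint, "describing postoperative complications other than PPCs in the first 5 postoperative days or hospital discharge whichever comes first". Section 11.3 names seven kinds of event and commits to assessing them: non-pulmonary sepsis, deep venous thrombosis with or without pulmonary embolism, myocardial infarction, acute pulmonary edema, cardiac arrest, acute kidney injury and stroke. It gives no collection schedule.

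Section 5.2 gives the schedule:

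- Day 0: "IMV after discharge from the operation room, admission to ICU/PACU after surgery, PPCs".
- Later days: "On day 1,2,3,4 and 5 the following variables will be collected: any new admission to ICU; any new or prolonged IMV; PPCs".
- End of daily follow-up: it "is completed on the day of discharge or on day 5 if the patient is still admitted".
- Completeness: "The data mentioned above are considered essential to defined as" complete, for each patient's record.

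After the completeness sentence, section 5.2 describes a different form for patients with invasive mechanical ventilation (IMV) and/or ICU/PACU admission during follow-up. It includes the SOFA score and "extra-pulmonary organ failure (number and type"). Centers are asked for these data but may leave them out if the workload exceeds their possibilities. Once a patient returns to the ward, the ordinary follow-up form applies again. The day 28 assessment covers length of stay and in-hospital death only.

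**The concern.** A named secondary endpoint has no matching entry in the list that sites will work from and that data checks will use to decide whether a record is complete. An analysis plan cannot recover what was never collected. If the fields are missing or treated as non-essential, a blank can be read as no event, and the published rates would be too low. They would also be low by different amounts in different centers, depending on who completes the ICU/PACU form. Later repair is limited: each center collects for one week (section 3.2), and the information linking records to patients is destroyed at the end of monitoring (section 8.1).

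**Working it through.** The protocol states no figure on this point. Its one computed figure, the confidence interval width of 0.0119, concerns the primary endpoint and is not in question. The check is a comparison of endpoints with collection items.

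**Step 1. Match each secondary endpoint (5.1.2) to an item in 5.2.**

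| Secondary endpoint | Collection item in 5.2 |
|---|---|
| 1. Ventilation practice and mechanics | Ventilator settings and mechanics at induction and hourly; weaning variables |
| 2. Intraoperative adverse events | Number and type, throughout the procedure |
| 3. Complications other than PPCs | None in the day 0–5 list |
| 4. Hemodynamic management and PPCs | Blood pressure, heart rate, fluids, transfusion; PPCs daily |
| 5. ICU admission, lengths of stay, mortality | ICU admission daily; stay and death at day 28 |

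Only endpoint 3 has no item. For PPCs, section 5.2 points to the definitions section on each follow-up day; it never does so for the other complications.

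**Step 2. Read the completeness rule as widely as possible.** Suppose it covers everything in 5.2 before that sentence, not just the follow-up items. That adds preoperative biochemistry, intraoperative data and early postoperative vital signs with arrhythmias. None of the section 11.3 events appears there, and no postoperative creatinine or urine output is listed. The gap remains.

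**Step 3. Ask whether the ICU/PACU form fills it.** It falls short in three ways. It comes after the completeness sentence and may be omitted. It applies only while the patient is ventilated or in ICU/PACU, so ward days revert to the ordinary list. And SOFA or an organ-failure count does not identify a venous thrombosis, a myocardial infarction or a stroke as section 11.3 names them.

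**Step 4. Direction of the bias.** Let p be the true event rate and c the share of events recorded. If blanks count as no event, the expected reported rate is c × p, a relative error of c − 1, which is zero or negative. If sites collect only what is listed, c = f × g × h, where:

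- f is the share of events on days covered by the ICU/PACU form;
- g is the share of those in centers that complete it;
- h is the share that the form's items identify.

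The protocol gives none of the three. Each lies between 0 and 1, so c does too. With equal p, f and h, two centers' reported rates differ in the ratio of their g values, and a center that omits the form (g = 0) reports none. If the fields exist and are completed for everyone, c = 1 and there is no bias.

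**The case against.** The strongest reply is that one list is incomplete, which does not show that the data will go uncollected. Section 11.3 says the events will be assessed, section 5.1.2 fixes their window, the Summary has a general entry for postoperative variables and outcomes, and the source is the chart. The eCRF and Figure 2 are not shown and may contain the fields. This stands against one inference that a reader might draw, that the endpoint cannot be produced at all; the document does not support that. It does not remove the point, because a general entry and an unseen form do not override an explicit list with an explicit completeness rule.

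A reader might also infer that events would be seen only in ICU patients. That is too narrow: the separate form is triggered by ventilation or by ICU or PACU admission, and centers are asked to complete it.

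A third tempting reading is that the kidney-injury rule cannot be met because one criterion runs "within 7days or increase in serum creatinine" while observation stops at day 5 or discharge. This fails. Seven days is the longest interval allowed for one of three alternatives. A 50% rise reached by day 5 qualifies, and the other two criteria need only 2 days and 6 hours. A rise first reached on days 6–7 lies outside the endpoint's own window anyway. Nor should the kidney-injury denominator be limited to patients with a postoperative creatinine: oliguria alone qualifies, so some cases would be excluded.

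**Conclusion.** The point holds as an internal inconsistency. Sections 5.1.2 and 11.3 promise an endpoint that the day 0–5 list and the completeness rule in section 5.2 leave out. As written, a ward record can be complete with no data on secondary endpoint 3, so its capture is not assured.

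The downward bias, and its variation between centers, rest on two assumptions: that sites follow the stated list, and that unrecorded events are counted as absent. No percentage can be attached, since the shares it depends on are not in the protocol. The damage is confined to one descriptive secondary endpoint; the primary endpoint, its collection and the sample size are unaffected. It is still worth correcting before collection starts, because the remedy is cheap then and limited later.

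**What to change.** Add the section 11.3 complications to the day 0–5 follow-up list in section 5.2 for all patients, each as yes/no with day of onset, taken from the chart. Include them in the data that define a complete record, so that sections 5.1.2, 5.2 and 11.3 agree. An explicit no then becomes distinguishable from a blank. If the eCRF already has the fields, only the protocol wording and their mandatory status need changing.

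The cost is a few more chart-based fields per patient and a short text amendment. The kidney-injury definition needs no change on this account.
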